## 10. SAMPLING

- This is powered as a superiority trial.
- For computer aided detection, the ADR of competent but non-expert endoscopists is assumed to be 20% and we believe that CADe will increase it to 30% (expert level). In order to demonstrate a difference of 10% between the two groups with an 80% power and a significance level (alpha) 0.05; we will need 588 patients (294 per group). We will over recruit by 10% (max total of 654) to allow for drop outs, poor bowel prep, incomplete dataset etc. Interim analysis will be done after 50% recruitment
- For computer aided diagnosis, the NPV of endoscopists is assumed to be 75%, and we believe the NPV of endoscopist plus CADx will be 90%. To achieve this with an 80% power and significance level (alpha) of 0.05, we will need to assess 200 diminutive recto-sigmoid (100 per group) polyps (588 total polyps), in an estimated 168 patients. We will plan to over recruit by 10% to allow for incomplete data (220 diminutive recto-sigmoid polyps, 647 total polyps). Interim analysis will be done after 50% recruitment

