# 2. SYNOPSIS

Study Title	Real time computer aided detection and characterisation of colorectal polyps; a prospective multi-centre randomised controlled superiority trial (ColoVision)
Internal ref. no.	PHU/2022/09
Problem statement	Colorectal cancer is a major health problem. Most colorectal cancers develop from precursor lesions (polyps), and early detection and removal of these polyps can reduce rate and improve outcome of colorectal cancer.
	Colonoscopy is the gold standard test to detect and remove polyps, however there is still significant polyp miss rate. Moreover, the concept of optical diagnosis of polyps has been recommended by various guidelines, however its implementation outside expert and academic centres is still limited.
	Computer aided detection (CADe) and computer aided diagnosis (CADx) of polyps is rapidly progressing and recent studies have shown promising results. However, there is still lack of high-quality data from well-designed and implemented randomised trials and hence the need for this study.
Research question / hypothesis	Our hypothesis is that the CAD device used in this study (WISE VISION®) can significantly improve endoscopists' adenoma detection rate (ADR) as well as their real time optical diagnosis to reach PIVI threshold of 90% NPV, compared to endoscopists not using the CAD device.
Study Design	This is an investigator initiated and led multi-centre randomised control superiority trial. The study will be using the NEC WISE VISION® device which has two functions: CADe and CADx and we will assess the impact of both.
	Participants will be randomised into two groups. The control group will have a standard colonoscopy (without CAD device support), and the intervention group will have colonoscopy with CAD device (both CADe and CADx)
	All patients (both in control and intervention group) will receive standard care. All decisions taken during the colonoscopy procedure will be taken by the endoscopists as per standard protocols.
Study Participants	Patients undergoing a colonoscopy

Planned Sample Size	CADe: 654 participants				
	CADx: 200 diminutive rectosigmoid polyps (588 total polyps)				
Follow-up duration	28 days (+/- 14 days)				
Planned Study Period	12 months				
Primary Objective	
 
To evaluate the impact of the CAD system on endoscopists' detection of colorectal polyps
 
				

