## Secondary End points

COLOVISION Protocol v1.0 18/08/2022 IRAS ID: 313559 Polyp detection rate (PDR) in both groups

Adenoma per colon (APC) in both groups

PIVI-1: agreement between surveillance interval decisions based on histology and that based on the combination of histology of non-diminutive polyps and optical diagnosis in both arms

Diagnostic performance measures in both groups (sensitivity, specificity, accuracy, NPV, PPV, AUC)

Diagnostic performance measures in both groups (sensitivity, specificity, accuracy, NPV, PPV, AUC) according to endoscopists experience

Diagnostic performance measures in both groups (sensitivity, specificity, accuracy, NPV, PPV, AUC) according to endoscopy imaging mode (WLI or EI)

The proportion of histological assessments that could have been avoided in both arms

The proportion of polyp removals that could have been avoided in both arms

Withdrawal time in both groups

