# 9. STUDY PARTICIPANTS

### 9.1 Study Setting

This will be an international multi-centre trial being carried out at several secondary care endoscopy sites across Europe. All endoscopists working on the study at participating sites will have access to and be trained in the use of WISE VISION® device.

The trial will run at the following sites:

- Queen Alexandra Hospital, Portsmouth, UK (Sponsor & lead UK site)
- Royal Sussex County Hospital, UK
- St Georges Hospital, UK
- King's College Hospital, UK
- Humanitas Research Hospital, Milan, Italy
- GastroZentrum Lippe, University Medical Centre Mainz, Germany
- Sapienza University of Rome, Italy

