### 11.3 Randomisation

Participants will be randomised electronically in a 1:1 ratio into two groups. The intervention group will have their colonoscopy performed with the assistance of the WISE VISION® CAD system, the control arm will have standard colonoscopy. Randomisation will be carried out prior to the procedure being started. The randomisation will be stratified by site to ensure an equal allocation in each centre. Additionally, a blocked randomisation, with varying block sizes, will be performed to allow for a balance between groups throughout the trial.

The randomisation process will be managed using the built-in module within the project's REDCap eCRF database managed by Portsmouth Hospitals University NHS Trust. The Data Manager will generate the randomisation allocation table using statistical software, which will then be uploaded into REDCap before the first patient is consented.

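### The ADR sample size assumes non-expert endoscopists, but the protocol neither limits participation to them nor stratifies by experience, so the 80% power is conditional on an unstated operator mix

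*Protocol*

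**What the plan says.** Section 10 (Sampling) ties the planning rates to a type of operator: "the ADR of competent but non-expert endoscopists is assumed to be 20% and we believe that CADe will increase it to 30% (expert level". With "80% power and a significance level (alpha) 0.05" it concludes "we will need 588 patients (294 per group" and then adds a margin: "We will over recruit by 10% (max total of 654".

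On who performs the procedures, Section 9.1 says only this: "All endoscopists working on the study at participating sites will have access to and be trained in the use of WISE VISION". That is a requirement for access and training, with no experience or baseline-ADR criterion. Section 9.3 lists criteria for patients and procedures, not for operators.

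Section 11.3 gives one stratification factor: "The randomisation will be stratified by site to ensure an equal allocation in each centre". Section 11.4 records the endoscopist's experience as a lifetime procedure count. Section 8.2 uses it for one set of secondary endpoints, the diagnostic performance measures "according to endoscopists experience". Section 14.2 compares ADR between arms with a chi-square test and mentions no adjustment.

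**The concern.** The premise of the sample size and the design describe different sets of operators. The planned 10-point gain lifts non-experts to a rate that the protocol itself labels expert level. On those figures an expert's control procedure already has the ADR that CADe is expected to produce. Because experience is recorded and used as a breakdown, the protocol evidently expects it to vary.

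If endoscopists near 30% take part and gain less than 10 points, the overall ADR difference shrinks. The trial could then miss a real benefit among less experienced operators. Even if they gain the full 10 points, both rates move towards 50%, the variance rises and power drops slightly. With site as the only stratum, nothing in the randomisation guards against a chance imbalance in experience between arms within a site.

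**Working it through.** **Inputs from the protocol.** Control ADR 20%, CADe ADR 30%, alpha 0.05, power 80% (Section 10); 1:1 allocation (Section 11.3). Sidedness is not stated; a two-sided test reproduces the sample size.

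**Inputs that are assumed.** The share *f* of procedures done by endoscopists with a control ADR of 30%, and their gain *g* from CADe. The protocol gives neither, so a range is shown.

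**Step 1: reproduce the stated size.** With p̄ = (p₁+p₂)/2 and d = p₂−p₁:

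n per group = [1.96·√(2p̄(1−p̄)) + 0.842·√(p₁(1−p₁)+p₂(1−p₂))]² / d²

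For 0.20 vs 0.30: [1.96×0.6124 + 0.842×0.6083]² / 0.01 ≈ 293.2, rounded up to 294 per group and 588 in total. Over-recruitment: 588/0.90 = 653.3, rounded up to 654. Both match Section 10.

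Power = Φ{[d·√n − 1.96·√(2p̄(1−p̄))] / √(p₁(1−p₁)+p₂(1−p₂))}. At n = 294: Φ{(1.7146 − 1.96×0.6124)/0.6083} = Φ(0.846) = 80.1%.

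**Step 2: overall power for a mix of operators.** Control ADR = 0.20(1−f) + 0.30f. CADe ADR = 0.30(1−f) + (0.30+g)f.

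Worked case, f = 20%, g = 0: control 0.20×0.8 + 0.30×0.2 = 0.22, CADe 0.30, d = 0.08. Power = Φ{(0.08×√294 − 1.96×0.6203)/0.6177} = Φ(0.252) = 60.0%.

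| Share f | Gain g (points) | ADR, control vs CADe | Difference (points) | Power at 294 per group | n per group for 80% |
|---|---|---|---|---|---|
| 0% | – | 20% vs 30% | 10 | 80.1% | 294 |
| 20% | 0 | 22% vs 30% | 8 | 60.0% | 471 |
| 20% | 5 | 22% vs 31% | 9 | 69.7% | 377 |
| 20% | 10 | 22% vs 32% | 10 | 78.1% | 309 |
| 50% | 0 | 25% vs 30% | 5 | 27.3% | 1251 |
| 50% | 5 | 25% vs 32.5% | 7.5 | 52.0% | 571 |
| 50% | 10 | 25% vs 35% | 10 | 75.5% | 329 |

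**Step 3: does the 10% margin absorb it?** If all 654 were analysed (327 per group), a 20% share with no gain gives about 65%, and a 50% share with a 5-point gain about 56%. The margin is in any case meant for drop-outs and incomplete data.

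**Step 4: power within non-experts at the same total.** Non-expert procedures per group are 294(1−f). At f = 20%: 294×0.8 ≈ 235, and power for 20% vs 30% is 70.8%. At f = 50%: 147, power 50.8%. The 80% figure therefore cannot simply be moved to the non-expert subgroup.

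**The case against.** The strongest reply is that any loss of power is conditional. A reader might infer that experts will take part and will dilute the effect. The protocol does not say so: it gives no expert share, and Section 9.1 does not state who may work on the study. The site list includes university and research hospitals, but the same section calls the sites secondary care. Nor does the protocol say that CADe stops helping at 30%. If experts also gain 10 points, there is no dilution and power falls only to 78.1% or 75.5%. All of this stands. The point is therefore an unsecured premise, not a demonstrated loss.

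A reader might also infer that the hypothesis concerns non-experts only, so that the trial misses its own target group. It does not. The Synopsis hypothesis and the Section 7.1 objective refer to endoscopists in general, and the primary comparison answers that question. Enrolling all endoscopists is a legitimate pragmatic choice. Nor does the Synopsis remark that "its implementation outside expert and academic centres is still limited" help: it refers to optical diagnosis, not detection.

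Finally, an ADR analysis by experience could sit in a statistical analysis plan that is not shown, so its absence from Section 14.2 is not in itself a defect. The stratification factor and the basis of the power statement, however, are fixed in this protocol. Section 11.3 has the allocation table loaded before the first consent, so a later plan cannot change the strata it contains.

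**Conclusion.** The point holds in a limited form. The sample-size arithmetic is correct, but its 80% power belongs to a set of operators that the design does not secure. In every mixed scenario examined, power at 294 per group is below 80%: 60% to 78% at a 20% share of endoscopists already at 30%, and 27% to 76% at a 50% share. Where the trial falls in these ranges depends wholly on the assumed share and gain. Section 10's own wording, with CADe raising ADR to expert level, makes a gain of less than 10 points for experts the more natural reading, but the protocol does not state it. This is a worthwhile and inexpensive improvement, not an error that invalidates the design.

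**What to change.** - **Section 11.3:** add experience class (non-expert or expert) as a second stratification factor. Define it by a cut-off on the lifetime procedure count already recorded under Section 11.4, and fix the cut-off before the first patient.
- **Section 14.2:** compare ADR with a test stratified by, or adjusted for, site and experience class, and report the ADR difference with its confidence interval within each class.
- **Section 10:** state that 80% power holds only if essentially all 294 procedures per group are by non-experts. Give the expected mix, the assumed ADR in each arm for each class, and the resulting overall power. Do not claim 80% power for the non-expert subgroup at the same total (about 71% if experts do 20% of procedures, 51% if they do 50%).

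Stratification balances the arms and supports the results by class; it does not undo dilution. If the power for the expected mix is judged too low, only a larger sample addresses that; Step 2 shows the sizes.

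Cost: one stratification factor, one analysis line and a qualified power statement. The endoscopist must be known when the patient is randomised, and the stated power becomes less favourable. Restricting who may operate would also align premise and design, but it narrows the trial's applicability and is a trade-off for the sponsor, not a recommendation here.

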## 8.2 Primary and Secondary Endpoints/Outcome Measures

## **Primary End points**

Adenoma detection rate in both arms PIVI-2: NPV of adenoma diagnosis in diminutive (<5mm) recto-sigmoid polyps in both arms

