# 18. STUDY SPONSORSHIP, MANAGEMENT & OVERSIGHT

Portsmouth Hospitals University NHS Trust shall act as Sponsor for the UK sites only. A research fellow will be responsible for overseeing the study and data collection, acting as the Trial Co-ordinator (TC). The TC will also be responsible for co-ordinating the set-up of the study at the international sites.

The study will also have a dedicated Trial Manager who will work alongside the Trial Coordinator to ensure the study runs efficiently and according to protocol and relevant Sponsor and study specific Standard Operating Procedures (SOPS).

A Trial Management Group (TMG) will convene quarterly and will oversee the day-to-day coordination and progress of the study. The TMG will consist of study representatives selected from the Chief Investigator which will include the Trial Co-ordinator (TC), Trial Manager (TM), and Research Nurses based at the lead/Sponsor site. The TM & TC will manage the project across all sites; ensuring co-ordination and communication between organisations. The TMG will be the primary point of contact for the study with responsibility for the delivery of approvals and permissions; initiation and training of sites, adverse event and progress reporting to the Sponsor and Trial Steering Committee (TSC), data collection, close-out procedures and archiving. The Trial Manager & Trial Co-ordinator will ensure all preparatory REC work is conducted, and coordinate NHS permissions with each UK site. All relationships and any delegation of duties will be formalised in written agreements facilitated by the Sponsor.

A Trial Steering Committee (TSC) will be set-up at the start of the study and shall convene to oversee the running and performance of the study against its key milestones at appropriate

intervals during the study. This committee will include an independent clinician as Chair of the committee, along with the Chief Investigator, independent clinicians, representatives from the TMG, Sponsor representatives and independent lay members. Safety events will be reviewed by the TSC with oversight and management of these by the Sponsor's research governance team.

Timeline	1-3	3-6	6-9	9-12	12-18	18-24	
(months)							
Study set up	Study set up						
Protocol							
development							
Collaboration with							
PPI steering group							
Submission for							
ethics and R&D							
approval							
Recruitment							
Patient invitation							
and recruitment							
open at QAH							

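### Two primary endpoints are each sized at the full 0.05, with an interim stated under each, but the protocol gives no success rule, alpha split or interim level

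*Protocol*

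**What the plan says.** Protocol section 8.2 lists two primary endpoints: "Adenoma detection rate in both arms PIVI-2: NPV of adenoma diagnosis in diminutive (<5mm) recto-sigmoid polyps in both arms". Section 10 (Sampling) sizes each of them separately.

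- **ADR.** The assumption is that "the ADR of competent but non-expert endoscopists is assumed to be 20% and we believe that CADe will increase it to 30% (expert level"), and the size is set "with an 80% power and a significance level (alpha) 0.05; we will need 588 patients (294 per group"). Over-recruitment of 10% takes this to a maximum of 654.
- **NPV.** The assumption is that "the NPV of endoscopists is assumed to be 75%, and we believe the NPV of endoscopist plus CADx will be 90"%, and the size is set "with an 80% power and significance level (alpha) of 0.05, we will need to assess 200 diminutive recto-sigmoid (100 per group) polyps". These polyps are expected from an estimated 168 patients.

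Both paragraphs close with the same sentence: "Interim analysis will be done after 50% recruitment". No purpose, test, level, boundary or stopping option is given for that analysis.

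Two other places bear on how the endpoints relate. The hypothesis in the synopsis puts the ADR gain and the NPV threshold together in one sentence. Section 14.2 calls ADR the primary outcome, in the singular, gives it a chi-square test, and names no between-arm test for NPV as a primary endpoint.

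On oversight, section 18 describes a Trial Steering Committee: "This committee will include an independent clinician as Chair of the committee, along with the Chief Investigator", with independent clinicians, trial-management and sponsor representatives, and independent lay members.

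**The concern.** Three design facts are fixed in the protocol: two primary endpoints, the full 0.05 behind each sample size, and an interim analysis under each. The rule that would tie them to one overall error rate is not fixed, and the only significance level stated anywhere is 0.05. A team following the text literally could test ADR and NPV at 0.05 each, at the interim and again at the end, and report any significant result as a primary finding. A primary claim reached that way would not carry a 5% error rate.

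The choice also limits what can be repaired later. Splitting alpha between the endpoints would need more patients than the stated maximum. Requiring both endpoints would mean that the stated 80% is not the chance that the trial succeeds.

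The interim adds a practical question. The endoscopist knows whether the CAD device is in use, and detection and optical diagnosis depend on the endoscopist. If between-arm results at halfway reached people running the trial, later behaviour could change. The protocol does not say who sees them.

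**Working it through.** **1. Reproduce the planned sizes.** Inputs from section 10: 20% v 30% for ADR, 75% v 90% for NPV, alpha 0.05, power 80%. Sidedness is not stated; two-sided is tried first. With p̄ the mean of the two proportions,

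n per group = [1.960 √(2p̄(1−p̄)) + 0.842 √(p₁(1−p₁) + p₂(1−p₂))]² / (p₁−p₂)²

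- ADR (p̄ = 0.25): 293.2, rounded up to 294. Matches.
- NPV (p̄ = 0.825): 99.5, rounded up to 100. Matches.

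One-sided testing would give 231 and 79, and a continuity correction 313 and 113; neither fits. So both sizes are single-look, two-sided 0.05 designs with no allowance for a second endpoint or an interim test. The over-recruited total is 588/(1−0.10) = 653.3, rounded up to 654.

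**2. Two endpoints, one test each at 0.05, either one counting as success.**
- Independent: 1 − 0.95² = 0.0975.
- Upper bound under any dependence: 0.05 + 0.05 = 0.10.

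**3. Adding an interim test at 0.05 (an assumption; the protocol does not state it).** Under the null, the statistics at 50% and 100% information are bivariate normal with correlation √0.5 = 0.707.
- P(|Z₁| > 1.96 or |Z₂| > 1.96) = 0.0831 per endpoint (0.091 for a look at 25% information, 0.073 at 75%).
- Either of two independent endpoints: 1 − (1 − 0.0831)² = 0.159.
- With correlated endpoints, by simulation: about 0.155 at correlation 0.3 and 0.142 at 0.6. The sum bound is 2 × 0.0831 = 0.166.
- For contrast, a strict interim level (p < 0.001) with 0.05 at the end gives 0.0502 per endpoint.

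**4. Both endpoints required.** The error does not add across endpoints; it is at most the per-endpoint level. Joint power under independence is 0.80 × 0.80 = 0.64.

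**5. Splitting alpha, 0.025 each, single look.** The same formula with 2.241 in place of 1.960 gives 356 per group (712 patients) and 121 polyps per group (242). The figure of 712 exceeds the stated maximum of 654. At the planned sizes, power is about 71% for each endpoint.

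**6. What 50% recruitment means for NPV.** Half of 654 is 327 patients, but the CADx target is expected from about 168. A look triggered by overall recruitment would therefore fall after the NPV target is expected to be met. A look triggered by the CADx target would fall at about 100 polyps, or 84 patients. The text does not choose between them.

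**7. Check of a usable boundary.** Interim p < 0.00305 (|Z| > 2.963) and final p < 0.049 (|Z| > 1.969), with correlation 0.707, give a type I error of 0.0500. With the drift that gives 80.0% power in a single-look test (1.960 + 0.842 = 2.802), power is 79.85%, a loss of about 0.15 points.

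**The case against.** The strongest reply is that the protocol never says that the interim is an efficacy test or that it uses 5%. The 0.05 belongs to the sample-size calculation. Interim boundaries and alpha spending are commonly left to a statistical analysis plan, which is not shown here, and an O'Brien-Fleming-type plan changes the final level so little that single-look sizing does not show that no adjustment is intended. This stands. A reader might infer that all four tests are planned at 5% and that the error rate simply is 8% per endpoint and 16% overall; the document does not support that. Those figures are conditional.

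Second, sizing both endpoints at 0.05 is correct if both must succeed or if they are tested in a fixed order. The hypothesis can be read as needing both, and section 14.2 gives ADR the leading place. This also stands, but neither passage is a decision rule and they point in different directions: one treats the endpoints as a pair, the other puts ADR alone.

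Third, a reader might infer a definite CADx look at 84 patients. That is only one reading. A single look at about 327 patients is at least as natural, so the finding is that the trigger is ambiguous.

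Fourth, a reader might infer from section 18 that comparative interim results will go to the trial team. The section does not say who receives interim results, and the committee has independent clinicians and lay members besides its independent chair. What remains is only that access is not specified.

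**Conclusion.** The point holds in conditional form. What the protocol fixes is two primary endpoints, each sized for one test at two-sided 0.05, and an interim stated under each. What follows depends on a rule that it does not state:

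| Reading | Consequence |
|---|---|
| Either endpoint counts, no interim test | error up to about 10% (9.75% if independent) |
| Either counts, and the interim is also tested at 0.05 | 8.3% per endpoint, about 16% overall at worst |
| Both required, no interim test | no inflation across endpoints; joint power about 64% |

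The 9.75%, 16% and 64% assume independent endpoints. The 8.3% and 16% also assume a look at 50% information, which is uncertain for NPV. An unseen analysis plan may set interim boundaries. It could not apply an even alpha split within the 654 maximum and keep 80% power on ADR. The success rule is best settled where the sizes are set, before any comparative data are seen.

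**What to change.** In section 10, replace the two interim sentences with one statement, choosing between:

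- **Non-comparative interim.** Pooled ADR, polyp yield, data completeness and safety, with no between-arm test. Alpha stays at 0.05 and no power is lost.
- **One efficacy look, ADR only.** An O'Brien-Fleming-type boundary (interim p < 0.00305, final p < 0.049), with the trigger given as a number of patients (327 if half of 654 is meant) and results seen only by members independent of the trial team. The cost is about 0.15 points of power.

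Then state the success rule: either both endpoints are required, or a fixed sequence applies with ADR first and NPV tested, once and at its full target, only if ADR is significant. Align section 14.2 with the choice, since it now speaks of a single primary outcome.

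The change is one of wording and needs no more patients, but it has a price that should be stated. Under the both-required rule the chance of joint success, and under the sequence the chance of an NPV claim, is about 64% with independent endpoints, not 80%. Ranking ADR above NPV, or giving up an efficacy look, is a design choice for the sponsor, because section 7.1 lists both objectives as primary.

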## 11.4 Study Assessments

Baseline characteristics will be recorded for all participants. Basic demographics will be recorded to include:

- Age
- Sex
- Co-morbidities and ASA score
- History of previous polyps/bowel conditions

During the colonoscopy the following will be recorded in all patients:

- Endoscopist including level of experience (number of life time procedures)
- Indication
- Bowel preparation used and quality
- Use of sedation/general anaesthetic
- Procedure start and finish time and time of maximal intubation
- Comfort score
- Adverse events
- Polyps detected to include the endoscopists optical diagnosis and assessment of size, morphology using the Paris classification, site and details of their removal.
- Still image/video of polyp (where available)

For patients randomised to colonoscopy plus CAD the following additional data will be recorded:

- Total number of potential polyps identified by CADe
- CADx diagnosis of polyps identified
- Outcome of assessment by endoscopist e.g. confirmed as polyp, characterisation assessment

Post colonoscopy:

- Adverse events will be recorded
- Histology of any polyps removed will be recorded to correlate with the endoscopist/CADx assessment of the lesion.

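### The CADx sample size takes all diminutive rectosigmoid polyps as the NPV denominator, so 200 polyps give less than the stated 80% power

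*Protocol*

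**What the plan says.** The second primary endpoint (protocol section 8.2) is "PIVI-2: NPV of adenoma diagnosis in diminutive (<5mm) recto-sigmoid polyps in both arms". Section 10 sizes it on these assumptions: "the NPV of endoscopists is assumed to be 75%, and we believe the NPV of endoscopist plus CADx will be 90" per cent. It continues "To achieve this with an 80% power and significance level (alpha) of 0.05", and gives the requirement as "we will need to assess 200 diminutive recto-sigmoid (100 per group) polyps (588 total polyps), in an estimated 168 patients". A 10% uplift for incomplete data raises this to 220 such polyps (647 in total). The synopsis lists 200 diminutive rectosigmoid polyps as the planned CADx sample size.

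Histology is the reference standard. Section 11.4 says "Histology of any polyps removed will be recorded to correlate with the endoscopist/CADx assessment of the lesion". For the adenoma detection rate (ADR), the same trial enrols 588 patients, up to a maximum of 654.

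**The concern.** In a comparison of two NPVs, the units are the negative calls: polyps optically diagnosed as non-adenoma whose histology is known. Polyps called adenoma do not enter the calculation. The protocol's 200 is a subset by size and site of all polyps (200/588 = 34%, and 220/647 = 34%), so it includes polyps of either optical diagnosis. Section 10 has no step from polyps assessed to polyps called negative. The protocol gives no negative-call share, adenoma prevalence, sensitivity or specificity from which to build one. Polyps left in place have no histology and would reduce the denominator further, by an amount that cannot be put in figures from the document.

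At stake is the power claim for a primary endpoint. A team working to section 10 could count 200 polyps, treat the CADx target as met, and have materially fewer usable observations than the calculation requires.

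**Working it through.** **Inputs (protocol section 10).** Control NPV 0.75, intervention NPV 0.90, alpha 0.05, power 80%, 100 polyps per group (110 after the uplift). Sidedness is not stated; two-sided is used here because it reproduces the plan's figure.

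**1. Reproduce the plan's figure.** Pooled two-proportion formula, without continuity correction:

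n = [z(0.975)·√(2·p̄·q̄) + z(0.80)·√(p1·q1 + p2·q2)]² / (p2 − p1)²

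- p̄ = 0.825, so √(2 × 0.825 × 0.175) = 0.5374, and × 1.960 = 1.0532.
- √(0.1875 + 0.0900) = 0.5268, and × 0.8416 = 0.4434.
- n = (1.0532 + 0.4434)² / 0.0225 = 99.5, so 100 per group.

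This matches the protocol. Other variants do not: 97 unpooled, 113 with continuity correction, 79 one-sided. The 100 is therefore the number of units over which each NPV is taken.

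**2. Power when only a share f of the polyps is called negative.** With m = f × (polyps per group) negative calls per group:

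power = Φ{[0.15·√m − 1.0532] / 0.5268}

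For example, at m = 50: (1.0607 − 1.0532)/0.5268 = 0.014, giving 51%. The values of f are assumptions. They are taken as equal in both arms, with polyps independent and every negative call verified.

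| Assumed f | Power, 100 polyps per group | Power, 110 polyps per group |
|---|---|---|
| 0.5 | 51% | 55% |
| 0.6 | 58% | 62% |
| 0.7 | 65% | 69% |
| 0.8 | 71% | 75% |
| 0.9 | 76% | 80% (79.8%) |
| 1.0 | 80% | 84% |

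With 110 per group, 80% power needs f of about 0.91 (0.91 × 110 = 100).

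**3. Polyps needed for 100 negative calls per group.** 2 × ⌈100/f⌉ = 400 (f = 0.5), 334 (f = 0.6), 286 (f = 0.7).

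**4. What the full trial might supply.** This depends on what the 168 patients are.

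- If they are enrolled patients, the yield is 200/168 = 1.19 polyps per patient. Then 588 to 654 patients give about 700 to 779 polyps (350 to 389 per group). Power at f = 0.5 is 96% to 98%, and it stays at or above 80% down to f of about 0.29 (100/350) or 0.26 (100/389).
- If they are polyp-bearing patients, and 25% to 50% of those enrolled bear polyps (assumed), 588 patients give 588 × 0.25 × 1.19 = 175 to 588 × 0.50 × 1.19 = 350 polyps. Power is then about 45% to 75% at f = 0.5 and 59% to 88% at f = 0.7.

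**The case against.** The best defence is that 200 is a minimum and not a stopping point. Optical diagnoses are recorded in both arms for every participant, 588 to 654 people are enrolled for ADR, and nothing in the protocol ends CADx data collection at 168 patients. If all eligible polyps are analysed and 168 means enrolled patients, power is ample. Which polyps enter the analysis may also be settled in a statistical analysis plan that is not shown.

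This defence stands as far as the trial's eventual power is concerned. A reader might infer that the NPV comparison really has 50% to 65% power. The document does not establish that: it would require both an assumed negative-call share of 50% to 70% and an analysis confined to 200 polyps. Nor does it follow that a true effect would be missed four times in ten or more. With 200 polyps that needs a share of about 60% or lower; at 70% the miss rate is 35%, and at 80% it is 29%.

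The defence does not rescue the stated requirement. Section 10 and the synopsis present 200 polyps as the number that gives 80% power, and it does not. The 10% uplift is assigned to incomplete data, so it is not a conversion from polyps to negative calls.

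**Conclusion.** The point holds as an error of unit, not of arithmetic. The 100 per group is correct for negative calls but is attached to all diminutive rectosigmoid polyps. The direction of the error needs no outside figure: the stated sample gives less than 80% power at any share below 100% (200 polyps) or below about 91% (220 polyps).

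The size of the shortfall is conditional. It is about 51% to 71% power for shares of 50% to 80% if only 200 polyps are analysed, or 55% to 75% with 220. Independence of polyps is assumed. With 200 polyps in 168 patients there is some clustering, and positive correlation within patients would lower power further.

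A reader might also infer that the planned enrolment is bound to cover the gap. That is not supported either. It is comfortable if 168 counts enrolled patients and doubtful if it counts polyp-bearing ones, and the protocol does not say which.

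**What to change.** In section 10 and the synopsis:

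- Restate the CADx target as 100 histology-verified negative optical diagnoses per arm. Give the assumed negative-call share and the polyp count that follows from it (about 286 in total at 70%, 334 at 60%, 400 at 50%).
- State that the NPV analysis uses every eligible polyp from all randomised participants and does not stop at 200 or 220 polyps or at 168 patients.
- Say whether the 168 are enrolled or polyp-bearing patients, so that the expected yield from 588 to 654 participants can be checked against the new target.
- If verified negatives fall short, restate the power for the number obtained, without enrolling more.

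The cost is a rewording of two places and one stated assumption. Optical diagnosis and the histology of removed polyps are already collected in both arms, so no new data item is needed.
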